### **Specific Items That Will Be Monitored for Safety**

Adverse effects from growth hormone administration, subject compliance, drop outs

### **Frequency of Data Review**

Data will be reviewed every 4 weeks during trial and thereafter every 3-6 months.

### **Rules for Alteration of Study Design**

Not applicable

### **Selection Procedures to Minimize Toxicity**

Growth hormone will be administered subcutaneously once daily using a 12-week single group design. No placebo will be used. The 12-week duration was selected because of our previous trial with IGF-1 showing effects in standardized behavior scales in that duration, hence establishing proof of concept.

The dose of daily growth hormone varies with the indication for therapy. Approved doses of growth hormone range from 0.16-0.25mg/kg/week for growth hormone deficient patients (Grimberg et al.; 2016) and up to 0.47 mg/kg/week for patients born small for gestational age.

In our proposed trial, we expect a majority of our patients to be growth hormone sufficient and therefore similar to the population of children with idiopathic short stature treated with growth hormone. We will recommend a dose of 0.15mg/kg/week divided daily for 2 weeks as a starting dose to ensure safety and tolerance. The dose will then be increased to 0.3mg/kg/week for 10 weeks, an average growth hormone dose in children with idiopathic short stature. The growth hormone dose will be titrated based on IGF-1 levels monitored serially up to a maximum dose of 0.45mg/kg/week. (<http://www.ferringusa.com/wp-content/uploads/2018/07/ZOMACTON-PI-7-18.pdf> )

Drug dose is calculated on a mg/kg/week basis. Using Center for Disease Control average Weight-for-age statistics in typically developing children ages 2 to 15 years ([www.cdc.gov/growthcharts/cdc\\_charts.htm](http://www.cdc.gov/growthcharts/cdc_charts.htm)), the overall average weight across a representative sample of males and females in this age range is 30kg.

Average growth hormone dose for weeks 1-2:  $0.15\text{mg} * 30\text{kg per week} = 4.5\text{mg per week} = 0.6\text{mg per day}$

Average growth hormone dose for weeks 3-10:  $0.3\text{mg} * 30\text{kg per week} = 9\text{mg per week} = 1.3\text{ mg per day}$

### **Grading System to Evaluate Adverse Events**

We will apply NCI-CTCAE criteria for attribution of AE by means of the following descriptors and codes, following the NCI guidelines for their application.

unrelated to treatment 1  
unlikely related to treatment 2  
possibly related to treatment 3  
probably related to treatment 4  
definitely related to treatment 5

### **Procedures to Assure Data Accuracy**

Data will be stored only by study personnel and will be cross checked twice prior to saving data.

### **Suspension Reported to**

IRB and GCO

### **Anticipated Circumstances of Subject Withdrawal**

The following criteria will be used to identify possible adverse treatment events, which will indicate the need to halt active participation of the subject in the GH study

Withdrawal of Consent PI or any regulatory authority (IRB, or FDA) believe withdrawal is necessary for the subject's health, well-being, or best interests.

PI or any regulatory authority believe that withdrawal is necessary for the subject's health, well-being, or best interests.

Laboratory: any abnormality on any test with adverse event (AE, Common Terminology Criteria for Adverse Events, National Cancer Institute, scales) # 3 or greater at any time in the study.

Any AE of any sort (clinical, laboratory) # 4 will result in halting for the individual and also for the study as a whole.

### **Primary or Secondary Safety Endpoints**

The study will be halted\* if two patients experience stopping conditions. (Exceptions for this criterion: Patients who withdraw voluntarily for reasons not directly related to or intrinsic to the study, e.g. incidental considerations such as concerns about travel time to study visits, unexpected pregnancy in the family, etc. Clearly, patients who experience adverse effects during growth hormone treatment would count towards this criterion for whole study stopping).

In addition, the study will be halted if one patient experiences a serious related adverse effect (grade # 4 AE).

All safety data will be reported to the IRB, and FDA every six months, or, in the case of any major safety concern or question, immediately. If any study stopping condition occurs, this will be reported immediately and the study halted, pending review by IRB, and FDA, and until the decision by regulatory authorities to resume, suspend or close the study has been made.

\*Operationally, "halting" will ordinarily mean that no further screening of new subjects and no treatment initiation will occur until the safety issue has been investigated and resolved (i.e., a final decision has been made to resume, suspend or close the study has been made). Enrolled study participants who have no new symptoms or adverse effects will ordinarily be allowed to continue study observation or treatment without interruption while the safety issue is being investigated, unless it is the contemporaneous judgment of the PI or subsequent judgment of the IRB, or FDA that it is unsafe to do so, in which case all observation or treatment interventions will be suspended forthwith.

---

Data Monitoring Committee Description	Data Monitoring Committee.docx
DMC Charter Available	No
Will the Research Include Data Coordinating Center Activities?	No

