### **Provisions for Research Related Harm / Injury**

Serial evaluations by physician every 4 weeks during study and also safety parameters monitored by blood draws will reduce research related harm/injury.

An adverse event (AE) will be defined as any untoward medical occurrence in a study subject, temporally associated with the use of the experimental medication, whether or not considered related to the medication. An adverse event can therefore be any unfavorable and unintended sign (including an abnormal laboratory finding), symptom, or disease (new or exacerbated) temporally associated with the use of the experimental medication. A serious adverse event (SAE) will be defined as an AE that meets any of the following criteria:

results in death;

is life threatening;

requires inpatient hospitalization;

results in a persistent or significant disability/incapacity;

any other adverse event that, based upon appropriate medical judgment, may jeopardize the subject's health and may require medical or surgical intervention to prevent one of the outcomes listed above.

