### **Adverse Events Reporting**

The Principal Investigator (PI) will be responsible for the detection and documentation of events meeting the criteria and definition of an adverse event or serious adverse event, as provided in this protocol. During the study, when there is a safety evaluation, the investigator or team member will be responsible for reporting adverse events and serious adverse events. Each subject's parents/guardians will be instructed to contact the investigator immediately should the subject manifest any signs or symptoms they perceive as serious.

Clinical laboratory parameters and other abnormal assessments qualifying as adverse events and serious adverse events:

Abnormal laboratory findings or other abnormal assessments that are judged by the investigator to be clinically significant will be recorded as AEs or SAEs if they meet the definition of an AE. Clinically significant abnormal laboratory findings or other abnormal assessments that are detected during the study or are present at baseline and significantly worsen following the start of the study will be reported as AEs or SAEs. The investigator will exercise his or her medical and scientific judgment in deciding whether an abnormal laboratory finding or other abnormal assessment is clinically significant.

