Monitoring for AEs will be conducted during scheduled and unscheduled visits per clinical and laboratory assessments. General AEs will be graded by the National Cancer Institute (NCI) CTCAE scales (note: please see discussion immediately following for AEs with neurological signs and symptoms). Examples of possible AE grades for parameters which will be measured during treatment (shown in Table 3 Research Protocol PDF). Also, any AE that the PI deems serious, although not easily categorized in the National Cancer Institute grading system, will be considered # grade 3.

If a subject develops significant (CTCAE AE # 3 grade) neurological signs and symptoms (e.g. cerebrovascular event or peripheral neuropathy), they will be seen immediately for a comprehensive evaluation, appropriate treatment, and removal from active participation in the study. We will also apply NCI-CTCAE criteria for attribution of AE by means of the following descriptors and codes, following the NCI guidelines for their application.

unrelated to treatment 1  
unlikely related to treatment 2  
possibly related to treatment 3  
probably related to treatment 4  
definitely related to treatment 5

The following are the potential adverse events associated with GH and how we intend to monitor and prevent these occurrences.

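### The one-patient study halt is worded more narrowly under Primary or Secondary Safety Endpoints (serious and related) than in the two withdrawal lists (any grade 4 adverse event)

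*Combined protocol and SAP*

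**What the plan says.** The one-event study halt appears in three places.

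- **Section 9, Procedures for Investigator to Withdraw Subjects**, and **Anticipated Circumstances of Subject Withdrawal** in the safety-monitoring part use identical words: "Any AE of any sort (clinical, laboratory) # 4 will result in halting for the individual and also for the study as a whole".
- The third place, **Primary or Secondary Safety Endpoints**, which directly follows the second of these, first gives a two-patient halting rule. It then adds that "the study will be halted if one patient experiences a serious related adverse effect (grade # 4 AE". The next paragraph says: "If any study stopping condition occurs, this will be reported immediately and the study halted", pending IRB and FDA review.

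Three other provisions bear on how these are read.

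- Provisions for Research Related Harm / Injury defines an adverse event as one "temporally associated with the use of the experimental medication, whether or not considered related to the medication". It defines seriousness separately, by outcome: "A serious adverse event (SAE) will be defined as an AE that meets any of the following criteria".
- Grading System to Evaluate Adverse Events lists five attribution codes, from 1 (unrelated) to 5 (definitely related).
- Drug Administration describes a 12-week single-group design without placebo.

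The symbol before each grade number is printed as # in the available text. It is the same in all three statements of the rule, so the comparison does not depend on it.

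**The concern.** A study-level stopping rule should give one answer for a given event. Here the part of the protocol that sets out the study-level halting rules words its one-patient trigger more narrowly than the two withdrawal lists do. Staff who act on that sentence alone would ask whether the event was serious and whether the drug caused it, and could decide that no halt is due. The withdrawal lists ask neither question.

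The relatedness question matters most. With one treated group and no placebo, the investigator would judge the cause of a single event knowing that the child is on growth hormone and with no control rate to compare against. The protocol rates the risk to these children as greater than minimal. Whether new children start the drug while a grade 4 event is under review should not turn on that judgment.

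**Working it through.** The protocol gives no figure for this rule, so the check compares the texts.

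**1. What the withdrawal lists cover.** "Any AE of any sort (clinical, laboratory) # 4 will result in halting for the individual and also for the study as a whole" sets a grade threshold and nothing else. Because an adverse event is defined as one "temporally associated with the use of the experimental medication, whether or not considered related to the medication", unrelated events count. Laboratory events are named expressly.

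**2. What the Safety Endpoints sentence adds.** It keeps the grade 4 threshold and adds two conditions.

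- *Related.* Five attribution codes exist, but nothing says which of them count as related. Code 3 (possibly related) is the obvious point of dispute.
- *Serious.* In this protocol seriousness is not the same as grade 4. It is defined by outcome (death, threat to life, inpatient admission, lasting disability, or medical judgment of jeopardy). Adverse Events Reporting says that laboratory findings judged clinically significant "will be recorded as AEs or SAEs if they meet the definition of an AE", so such a finding need not be serious. The grading text also says that "any AE that the PI deems serious, although not easily categorized in the National Cancer Institute grading system, will be considered # grade 3", which ties seriousness to the grade 3 threshold, not to grade 4.

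**3. The two wordings applied to one grade 4 event in one child.**

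| Grade 4 event | Withdrawal lists | Safety Endpoints sentence read alone |
|---|---|---|
| Serious and related | study halts | study halts |
| Serious, unrelated | study halts | no halt |
| Not serious, related | study halts | no halt |
| Not serious, unrelated | study halts | no halt |

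The two agree in the first row and differ in the other three.

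**4. What differs in practice.** The affected child stops under the withdrawal lists in all four rows. As Primary or Secondary Safety Endpoints explains, a halt ordinarily means no new screening and no new treatment starts, while enrolled children without new symptoms carry on. The difference is therefore whether recruitment and new starts pause while the event is investigated. It can last only until a second child meets a stopping condition, when the two-patient rule halts the study anyway.

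**5. Whether the text ranks the wordings.** It has no explicit precedence statement. The Safety Endpoints sentence opens as an addition to the preceding rule and does not say that it is the only one-patient trigger. The following paragraph, "If any study stopping condition occurs, this will be reported immediately and the study halted", is general. An event that the adjacent list says halts the whole study is naturally such a condition. The combined reading therefore favours the broader rule.

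**The case against.** The strongest reply is that nothing conflicts. Every trigger is a sufficient condition, none is stated as exclusive, and a site following all three places halts on every grade 4 event. That is correct, and it is the better reading. A reader might infer that the narrower sentence overrides the lists, so that the plan as a whole allows an unrelated grade 4 event to pass without a halt. The documents do not support that. What remains is that, on the combined reading, the two qualifiers do nothing, and staff have to know to ignore them.

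A second reply is that the parenthesis defines the phrase, so that a serious related effect simply means a grade 4 event. That would reconcile the texts, but grade says nothing about cause, and the word *related* would still stand there without effect.

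A third reply is that the harm requires partial reading and is cushioned elsewhere. This stands. Major safety concerns must be reported immediately, and the PI, IRB or FDA may suspend all treatment.

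The Data Monitoring Committee description and the Research Plan PDF are listed as attachments but are not reproduced in the document. Either could settle the point.

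Two further inferences should be resisted. One is that a child with a grade 4 event could stay on treatment; the individual halt rules that out. The other is that the stopping conditions counted by the two-patient rule have no content; the list immediately before that rule is their obvious antecedent.

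**Conclusion.** The concern holds as a minor inconsistency in a safety threshold. The same decision is worded broadly in two places and narrowly in a third. The broader rule should prevail when all three are read together, but the narrower sentence gives a different answer for any single grade 4 event that is judged unrelated or does not meet the seriousness definition.

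No probability can be put on this. The documents give neither a grade 4 event rate nor the share of such events likely to be judged unrelated, so any figure would come wholly from assumed inputs and would also presume that the two withdrawal lists are disregarded. The conclusion rests on the visible text and on the # symbol meaning the same in each place.

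**What to change.** In Primary or Secondary Safety Endpoints, replace the trigger in the one-patient sentence with the one used in the two withdrawal lists: an adverse event of any sort, clinical or laboratory, at the same grade 4 threshold. State that the halt applies regardless of attribution or seriousness. Attribution is then judged in the IRB and FDA review that the same section already requires, after the halt and not as a condition for it.

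The two-patient rule and its exception for incidental voluntary withdrawal can stay as they are.

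The cost is a wording amendment with no new visits, tests or data. The downside is an occasional extra pause in screening and treatment initiation for an event later judged unrelated. Enrolled children without new symptoms would ordinarily continue during that pause.

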**23. Funding**

**Funding Source Name** Seaver Foundation

**Contact**

**Funding Category** Foundation

**Meditrack (<https://contracts.tractmanager.com/Contracts/Login.aspx>)** [Meditrack \(<https://contracts.tractmanager.com/Contracts/Login.aspx>\)](https://contracts.tractmanager.com/Contracts/Login.aspx)

**Grant or Contract Title** An Open Label Trial of Growth Hormone in Children and Adolescents with Phelan-McDermid Syndrome Targeting Social Withdrawal and Repetitive Behavior

**Grant or Contract Number**

**Funding Status** Funded

**Project Initiated By** Investigator

**Grant / Contract Principal Investigator (PI)** [name]

**Department** Pediatrics

**Department** Pediatrics

**Identify Substantive Differences Between Protocol and Funding Proposal**

## **24. Radiation Safety**

Study protocol involves any of the following Radiological Procedures requiring use of Dosimetry Chart Yes

*\* Radiological procedures that are administered in addition to those that the participant would receive as part of standard care (radiation above and beyond standard of care)*

*\* Radiological procedures that are administered solely for experimental or research purposes (would NOT be otherwise administered)*

*\* Standard of care radiological procedures that are being altered or performed differently for research*

*\* Use of radiological procedures that are the subject of the investigation (comparison studies)*

### ***Dosimetry Chart***

***Please fill out the chart and attach it below.***

Dosimetry Chart DOSIMETRY.xlsx

Study protocol involves any of the following Radiological Procedures No

*\* Use of an investigational radiopharmaceutical, or use of an approved radiopharmaceutical for an investigational purpose*

*\* Use of investigational radiotherapy, or use of approved radiotherapy for an investigational purpose*

*\* Use of fluoroscopy*

*\* Radiation exposure to children or pregnant women*

*\* Radiation exposure to healthy subjects (ADULTS)*

*\* Use of an investigational radiologic device (such as an experimental scanner), or use of an approved device for an investigational purpose*

Study protocol involves any of the following Standard of Care Radiological Procedures (including projects where discrete Standard of Care Imaging is acquired in addition to Research Imaging) Yes

*\* CT imaging*

*\* Nuclear medicine*

*\* Radiography*

*\* Fluoroscopy*

*\* Radiation-based therapy*

*\* PET/CT*

## **25. Drugs / Biologics**

Study Fund Account (or alternate departmental / fund account, if study is not yet established)	[REDACTED]
Generic Name	Recombinant Human Growth Hormone (Somatropin)
Brand Name	Uncertain at this point
Drug Has Valid IND	No
	For each drug / biologic with an IND number, ensure that the application includes one of the following. * Sponsor protocol with the IND number. * Communication from the sponsor or the FDA with the IND number.
IND Number	
Name of IND Holder	
Type of IND Holder	
Drug Meets One of the Following Categories for Exemption	Yes
	
Category 1: * The drug is lawfully marketed in the United States. * The research is not intended to be reported to the FDA as a well-controlled study in support of a new indication for use nor intended to be used to support any other significant change in the labeling for the drug. * The research is not intended to support a significant change in the advertising for the product. * The research does not involve a route of administration or dosage level or use in a patient population or other factor that significantly increases the risks (or decreases the acceptability of the risks) associated with the use of the drug. * The research is conducted in compliance with the marketing limitations described in 21 CFR §312.7. Category 2: * A clinical investigation for an in vitro diagnostic biological product that involves one or more of the following: (1) Blood grouping serum; (2) Reagent red blood cells; or (3) Anti-human globulin. * The diagnostic test is intended to be used in a diagnostic procedure that confirms the diagnosis made by another, medically established, diagnostic product or procedure. * The diagnostic test is shipped in compliance with 21 CFR §312.160. Category 3: * A clinical investigation involving use of a placebo when the investigation does not otherwise require submission of an IND.

Category for Exemption	Category 1
Justification for Meeting Criteria	
Growth hormone is FDA approved for use in children with growth hormone deficiency (including idiopathic [of unknown cause] growth hormone deficiency), Turner syndrome, Noonan syndrome, Prader-Willi syndrome, short stature homeobox-containing gene (SHOX) deficiency, chronic renal insufficiency, idiopathic short stature and children small for gestational age. (https://www.fda.gov/Drugs/DrugSafety/ucm237839.htm) This research is intended as a pilot clinical trial to look at social withdrawal and repetitive behavior in children with PMS and not as a new indication for GH treatment. Our study population will not have growth hormone administered for any of the FDA approved indications. The results of this study may warrant further such studies in the future. The dose of daily growth hormone varies with the indication for therapy. Approved doses of growth hormone range from 0.16-0.25mg/kg/week for growth hormone deficient patients (Grimberg et al.; 2016) and up to 0.47 mg/kg/week for patients born small for gestational age. In our proposed trial, we expect a majority of our patients to be growth hormone sufficient and therefore similar to the population of children with idiopathic short stature treated with growth hormone. We will recommend a dose of 0.15mg/kg/week divided daily for 2 weeks as a starting dose to ensure safety and tolerance. The dose will then be increased to 0.3mg/kg/week for 10 weeks, an average growth hormone dose in children with idiopathic short stature. We will obtain an exemption from the FDA IND for the use of growth hormone in this study. Neither the patients nor their insurances will be charged for growth hormone. The medication will be funded by the study and provided to families to administer daily at home.

To be a coordinating center, the Mount Sinai investigator is the Principal Investigator for multi-site participation in the trial. The Investigational Drug Service (IDS) may support trials as the coordinating center. IDS services include but are not limited to randomizing for other sites, storing and shipping drugs to participating sites, etc.

Icahn School of Medicine at Mount Sinai (ISMMS) Is the Coordinating Center	Yes
Role of the Investigational Drug Service (IDS)	Not applicable, single center study
Drug / Biologic Description (Manufacturer/Generic Name/Form/Strength)	Somatropin/recombinant Human Growth Hormone as a subcutaneous injection, typically sold commercially as 10mg/vial
Controlled Substance Schedule	No
Using Investigational Drug Service (IDS) Research License	In order for the Icahn School of Medicine at Mount Sinai (ISMMS) to be compliant with the regulations regarding controlled substance research, a New York State Department of Health-issued Researcher license and DEA-issued Researcher Registration Number must be on file for each trial using controlled substances. The Investigational Drug Service maintains these licences and will make them available to our investigators to support our research. Refer to www.health.state.ny.us/professionals/narcotic and http://firstclinical.com/journal/2011/1112_DEA.pdf for more information.
Use of this Drug / Biologic Is Considered Standard of Care	No
Requested Pharmacy Services	Dispensation, Storage, Label
Specify Other Requested Pharmacy Services	
Drug / Biologic Will Be Supplied By	Commercially Available/Sourced by Hospital
Specify Other Drug / Biologic Supplier	
Using Placebo	No
Placebo Will Be Supplied By	
Compounding Required (Paid for by Study Funds)	
Where Drug / Biologic Will Be Administered	Outpatient Clinic
Specify Location of Private Office	
Storage Requirements of Drug / Biologic	Refrigerated (2-8°C)
Where Drug / Biologic Will Be Stored	Patients Own Supply
ALL of the Following Storage Criteria Are Met	

\* The storage area is well maintained, provides adequate lighting, ventilation, sanitation, space and security. \* The temperature in the storage area is controlled and monitored using calibrated monitoring devices. \* The temperature monitoring system has sensors

for continuous monitoring and alarms set at the points representing the temperature extremes. \* Records of temperatures and alarms are maintained and all excursions outside the labeled storage conditions are appropriately investigated and reported to the sponsor.

